10.2.3 HIPAA Authorization and Medical Record Release Forms

Health records may be used preparatory to research, to identify individuals who are potentially eligible for study participation and to determine the timing of a potential participant's next PCP visit. For patient participants, a HIPAA disclosure will allow the study to access protected health information in the patient's medical record. Health records will be used for the collection of some study outcome measures (e.g., prescriptions and care received in the study clinic). This study will have a single IRB. Sites will be responsible for communicating with their local IRBs or Privacy Boards and obtaining the appropriate approvals or waivers to be in regulatory compliance.

10.3 Randomization

After providing written/electronic informed consent, PCPs will be randomly assigned in a 1:1 ratio to (1) STOP Intervention, or (2) Enhanced Usual Care (EUC). In study sites where PCPs practice in teams, randomization will be at the team level (for example, if PCPs practice in teams of two, the two PCPs will be treated as one cluster in the randomization). Randomization will be stratified by site and will occur at each site prior to the intervention start date. The randomization procedure will be conducted through a process set up by the CTN Data and Statistics Center (DSC), and the randomization sequence will be unknown to staff. The DSC statistician will review the randomization data on a regular basis to ensure that the scheme is being implemented according to plan.

Patient participants receive the intervention to which their PCP is assigned. While randomizing at the PCP level introduces the possibility of contamination that has the potential to reduce the observed intervention effect size, this strategy is similar to our study team's previous studies (TOPCARE randomized PCPs, QUIT randomized patients) that had significant findings. Contamination could arise if patient participants change PCPs or make appointments with PCPs in the opposite treatment arm, or if PCPs drop out of the study (which would force a change in PCP upon their patients). These instances of contamination will be recorded, and the contamination data may be summarized with the study findings.

After the baseline PCP encounter, differences in clinical care received by the patient participant are driven primarily by the NCM, who interacts directly with the patient participant and provides advice to the PCP about the patient participant's management. To guard against contamination, NCMs will be instructed to communicate only with PCP and patient participants who are in the intervention condition. To facilitate this, NCMs will have a list of patients who are enrolled in the study and have a PCP assigned to the intervention condition. In the relatively unlikely event that a patient participant in the EUC group has a visit with STOP intervention PCP after the baseline visit (for example, if the intervention PCP is covering for the patient's regular provider), the NCM will not interact with the patient participant.

10.4 Baseline Assessment

PCP participants complete self-administered (SA) questionnaires at baseline. These are completed as paper or electronic questionnaires prior to the beginning of the intervention period.

For patient participants, the baseline assessments are broken up into two parts: 1) a few baseline assessments are administered as part of the prescreener survey, for participants who prescreen eligible and 2) the remaining baseline assessments are administered during the baseline visit. The specific assessments are detailed in Table 6. Details regarding all assessments are in Section 11. Assessments are electronically self-administered or RA-administered as indicated; those that are RA-administered will be given in a private area of the clinic or may be done by phone.

Assessments that are most sensitive to change based on the brief advice delivered by the video doctor and/or PCP are included at the end of the prescreener survey for patients who prescreen eligible. So as not to interfere with time-pressured clinical workflows, patient participants can complete assessments that are less sensitive to change after the baseline visit. These assessments may be completed up to three weeks after the baseline visit, but most often will be done on the same day or within one week. The assessments administered after the baseline visit include questionnaires on demographics, mental health, sleep, social supports and health-related quality of life, and health services utilization. If possible, a urine sample will also be collected (either in-person or remotely) at the baseline visit.

10.5 Pilot Study

A pilot study will be conducted in 1 study site prior to initiation of the trial. The pilot site may participate in the main study, following completion of the pilot. The purpose of the pilot is to assess whether any adaptations are needed to facilitate patient recruitment, enrollment, or the collection of the baseline assessment, and only patient participants are enrolled in the pilot study. Eligibility requirements for patient participation are the same as for the main study, with the exception of the requirement that patients have a PCP who is participating in the study. The study procedures for patient recruitment and enrollment in the pilot will be the same as those detailed above for the main study.

Procedures for enrolled patient participants in the pilot will be the same as those used for the main study, except that pilot study activities will be limited to no more than four coaching sessions and two follow-up assessments, conducted at approximately 2- and 4-weeks post-baseline. Pilot study patient participants will not receive the full EUC or STOP intervention. Four telephone health coaching sessions (one per week after the baseline visit) may be conducted in order to test the mechanics of carrying out the sessions. Pilot patient participants may also be asked to participate in interviews, which may include cognitive interviews and question testing techniques that are intended to gather information about the feasibility and acceptability of the study procedures, assessments, and the STOP intervention. Interviews may also include assessing the acceptability of assessment procedures, and incentive payments for patient participants. The NCM and PCP brief advice components of the intervention will not be piloted, because introducing these practices into the clinic prior to the intervention start date is likely to contaminate the study (i.e., the NCM and PCPs would begin using their skills to manage opioid use with their other patients, who have not yet been enrolled). Given that both the PCP and NCM components have been tested in prior large trials (QUIT and TOPCARE), little new information is likely to be gained from a pilot. Instead, training of the NCMs will include role plays of clinical scenarios that will serve to build provider skills, while simultaneously refining the content and delivery of the clinical intervention. Training sessions, which are described in Section 12 and further detailed in a training

plan, will be led by members of the research team who have experience teaching and implementing these protocols with clinical staff.

The informed consent document used in the pilot will reflect the limited study activities for these participants. Individuals participating in the pilot will receive a monetary incentive for participation. The research team may enroll up to a limit of 50 patient participants. The higher number of pilot patient participants will be used if there is a need to adapt and test alternative approaches to the recruitment, enrollment, and assessment procedures, or if additional interviews are needed to inform feasibility and acceptability.

10.5.1 Additional Telephone Health Coaching for Training Purposes

In addition to the pilot activities described above, the pilot site will also recruit up to ten patients to participate only in the telephone health coaching component of the pilot study. The purpose of this activity is to collect additional information and feedback on the coaching sessions, in order to better inform training activities for the health coaches in the main study. Patients will be offered a total incentive of \$50 to participate in this activity. Participants will receive up to four coaching sessions and the content and structure of the sessions will be the same as what is described in Section 10.6. No data will be entered into eClinical for this activity. Patients will be asked to verbally consent to recording of the coaching sessions, and research staff will document consent at the bottom of the script. The inclusion criteria for this activity are listed in Section 8.1.2.

Patients may be referred to participate in this activity by their PCP or other clinical staff at the pilot site. Research staff may also invite participants who prescreen eligible for the pilot study, but are not eligible (i.e., screen ineligible) for the pilot study, or those who screen eligible but do not wish to enroll. Participants receiving telephone health coaching only will provide verbal consent to participate in the coaching sessions using an IRB approved verbal consent script. They will not complete any self-administered forms or surveys; they will be contacted by the RC/RA approximately two weeks after completing their last coaching session in order to participate in a brief feedback interview over the phone.

10.6 Study Treatments

Interventions used in the study are described below. Training, supervision, and fidelity monitoring procedures for the interventions are described in Section 12, and in more detail in the Training Plan.

Patient participants in either arm who develop a moderate-severe OUD, based on the clinical judgment of the PCP, NCM, or telephone health coach at any time during the study can be offered clinical care to address OUD. This care may include office-based treatment using medication for OUD (MOUD) and referrals to addiction treatment. In the EUC arm, clinical care for OUD is facilitated by clinical staff (for example, PCPs, behavioral health providers, or social workers), while in the STOP arm clinical care for OUD is facilitated by the NCM or other clinical staff. Clinical guidelines for identifying OUD will be provided in the study MOP, and procedures for linking patients to OUD treatment will be included in the site operating procedures (SOP).

10.6.1 Enhanced Usual Care (EUC)

In the **EUC arm**, PCPs will conduct primary care as usual, without the support of the NCM. At the baseline visit, patient participants receive educational materials and view a short video. The educational materials include information about preventing opioid-related overdose, including how to obtain a naloxone kit; and a handout on cancer prevention. The video content will feature information on cancer prevention. It will be viewed on a tablet or desktop computer and will be approximately 2 minutes long. All EUC patient participants receive the same video, which is not tailored to the responses given on their questionnaires. There is no study intervention after the baseline visit.

There are no limitations placed on primary care treatment as usual. The EUC condition enhances usual care by providing patient participants with an OD prevention educational handout. This is done for safety reasons, because the current standard of care in most primary care clinics is to offer no universal screening for opioid use or OD prevention interventions in primary care. The local research teams at each site will ensure that information on naloxone is detailed and specific, and that the pamphlet gives clear guidance on how to access naloxone. The content will be further detailed in the manual of procedures and/or site standard operating procedures.

10.6.2 STOP Intervention

In the **STOP arm**, enrolled patient participants will receive the intervention components of brief advice from their PCP and/or a video doctor, printed educational materials, and will be asked to interact with the NCM and receive telephone health coaching. The roles of the intervention team members are summarized in Table 4 and further detailed below.

Telephone Health Coaches, Nurse Care Managers and research staff will use a HIPAA compliant communication software called QliqSOFT to coordinate care for STOP intervention patient participants.

Baseline primary care visit

Patient participants in the STOP arm will receive brief advice, consisting of PCP-delivered counseling and/or viewing a “video doctor.” For in-person visits, the video doctor can be completed either in-person or remotely. For telehealth visits, the video doctor will be sent via email or text to the patient participant. They will additionally receive an educational pamphlet about opioid overdose prevention and an introduction to the role of the NCM and telephone health coaches.

PCP brief advice

Brief advice can be delivered by the patient participant’s PCP as part of the baseline visit or within 10 business days. Before providing the patient participant with the brief advice, PCPs will receive a printed summary report from the RC/RA or clinical staff. The summary advises the PCP that their patient participant screened positive for risky opioid use, lists the patient participant’s screening results (TAPS Tool +/- COMM) and gives a suggested counseling script. The counseling script will include specific advice on opioid-related risks, (e.g., developing addiction, physiologic dependence, and overdose prevention), will inform patient participants of resources

to help them reduce their risk (NCM and telephone health coaching), and will include a recommendation to reduce their risk behavior. PCPs will be trained in using this script to deliver counseling, which is intended to last approximately 3 minutes. In the QUIT trial, two-thirds of the interventions lasted at most 3-4 minutes; only three (1.5%) required more than 10 minutes. PCPs will not be incentivized for delivering this counseling.

Video Doctor: The video doctor should be completed as part of the baseline visit. If the patient participant sees their PCP during the baseline visit, they will view the Video Doctor after they see their PCP and before they complete the baseline assessments. If the patient participant does not see their PCP as part of the baseline visit, the RC/RA will show them the Video Doctor after consent and enrollment. For telehealth or remote visits, the video link may be sent via email or text to the patient participants. The video is a recording of a provider delivering brief advice about opioid use that includes the same elements covered in the summary report outlined above, and will be specific to use of illicit or prescribed opioids. The video may also include an introductory message from the site NCM and the telephone health coach(es).

Patient participants in the STOP intervention will receive an educational pamphlet, which includes information about preventing opioid-related overdose, including how to obtain a naloxone kit. Patient participants will also receive a printed handout with information about the NCM and telephone health coaching sessions, including the benefits and expectations of their participation, schedule of research visits and telephone health coaching sessions, and contact information. When possible, the NCM will introduce themselves to the patient participant in-person during the course of the baseline visit. The NCM may reach out to the patient participant following the baseline visit (by phone, email, text message, or via the patient portal) to introduce themselves.

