3.3.4 Baseline Value

The baseline values for HLM, TAPS Tool, Current Opioid Misuse Measure (COMM), and Readiness to Change assessments are collected in the prescreening survey and all other baseline values are collected at the screening and baseline visits.

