Overdose risk behavior at Baseline	COREVARS.ORBSCR (ORB)	continuous	Score to measure overdose risk behavior at baseline
Pain severity at Baseline	COREVARS.BPISCR_SEV (BPI)	continuous	Score to measure pain severity at baseline
Pain interference at Baseline	COREVARS.BPISCR_INT (BPI)	continuous	Score to measure pain interference or functioning at baseline
Anxiety symptom at Baseline	COREVARS.PMASCR (PMA)	continuous	Score to measure anxiety symptoms at baseline
Depression Symptoms at Baseline	COREVARS.PHQSCR (PHQ)	continuous	Score to measure depression symptoms at baseline
Sleep quality at baseline	COREVARS.PMSSCR (PMS)	continuous	Score to measure sleep disturbance at baseline
Health-related Quality of Life at Baseline	COREVARS.SFMSCR (SFM)	continuous	Score to measure overall health-related quality of life at baseline

¹ Covariates that are calculated or scores are in the COREVARS analysis dataset and are derived from the data from the form name listed in parentheses.

The aim of covariate adjustment is not to determine the true relationship between covariates and the primary outcome variable but to provide an unbiased estimate of the true treatment effect. The regression model is based on a linear relationship between the covariates and the primary outcome when the covariate is continuous. However, increasing the number of covariates can decrease the power of the study and cause collinearity, so the following steps will be taken to identify the covariates to be included in the regression model:

1. Include the two covariates of site (stratification factor) and baseline value of response as identified in the primary outcome analysis model in Section 7.2.2.
2. Include all covariates from Table 3 that will result in 70% or more of the ITT population being included in the analysis. Since the mixed effect model will remove the entire patient record from the analysis if it is missing any covariate value, covariates with a significant amount of missing data will be removed.

3. Run correlation analyses among the covariates, and select the covariate set with low or moderate correlation to avoid collinearity and provide efficiency gains.

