This table will be repeated by visit and prescription for opioids in the past 6 months (yes/no) as reported on the COMM. The table will present the number and percentage of participants at that visit that reported having an opioid prescription in the past 6 months. If a patient participant does not complete the COMM assessment at that visit, the previous COMM response will be used to determine if the patient participant has an opioid prescription. For example, if the patient participant does not do the 12-month COMM assessment but has a 12-month UDS, the COMM response from the 6-month visit will be used to categorize the participant at the 12-month visit. If

the patient participant does not have any COMM responses from the baseline, 6 or 12-month visits but has UDS collected for those visits, it will be assumed the patient participant does not have an opioid prescription for any of the visits.

The following analysis will be done by the LN:

The proportions of individuals whose average number of days (within 30 days) of illicit or nonmedical opioid use during 180 days of follow-up increased relative to their baseline measure (days of use in the 30 days before the baseline assessment, H2.6) will be compared between groups at 6 months and 12 months using chi-square test respectively.

Descriptive summary statistics for COMM score assessed at screening and at 6 and 12 months (H2.7 h), Comparisons of the secondary outcomes between the two treatment arms will be conducted using t-tests or Mann-Whitney tests for continuous measures, chi-square tests for categorical measures.

Generalized estimating equations (GEE) to account for correlation of responses within PCP cluster will be fit for the incidence of moderate to severe OUD (defined as a score of at least 4 on the CIDI, H2.8) and drug use disorder (PDSQ drug items, H2.9) and alcohol use disorder (PDSQ alcohol items, H2.9) assessed at 6 and 12 months separately. Treatment effect is estimated adjusting for baseline level of each measurement. Time trend is evaluated using a time variable.

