Self-reported overdose risk behavior will be measured by the overdose risk behavior questionnaire (which gives a numeric score) at baseline, 6, and 12 months. Mean scores will be compared between groups at 6 and 12 months in a random-effect regression model. Also, the total number of non-fatal opioid-related overdose events in the past 3 months will be measured at baseline, 6, and 12 months. Mean numbers of opioid-related overdose events will be compared between groups in a random-effect regression model (H 2.10).

Changes in pain-related symptoms and functioning from baseline as measured by the BPI (which calculates a numeric score) will be compared between treatment arms using Mann-Whitney tests. As the scientific goal is to demonstrate no worsening of pain, a noninferiority test will compare changes in BPI score between treatment and control groups with a minimal clinically important difference of 1 based on the IMMPACT recommendations. A secondary analysis will distinguish the effect of STOP on the change in pain-related symptoms for participants with opioid prescriptions at baseline, and the effect for those who were enrolled solely due to illicit use.

Symptoms of depression, suicidality, anxiety (H2.12), and poor sleep (H2.13) in the past two weeks will be measured at baseline and quarterly (PHQ-8) and at baseline, 6, and 12 months (PROMIS anxiety and sleep measures and PSS). Mean values will be compared between treatment arms in random-effect regression models.

Health-related quality of life (H2.14), and ED and hospital utilization (H2.15) in the past two weeks will be measured at baseline and at 6 and 12 months. Mean values will be compared between treatment arms in random-effect regression models.

Similar models will be fit for the Aim 3 objectives, but these will use provider rather than patient as the unit of observation, so will not need a PCP effect to adjust for within-PCP correlation. Regression models will be used to compare number of prescriptions of high-dose opioids within 12 months of follow-up between treatment arms as well as number of days prescribed during 12 months follow-up. Similar analyses will be done for number of prescriptions for any opioids or benzodiazepines, numbers of naloxone kits prescribed, numbers of urine toxicology tests ordered and completed, and number of patient participants receiving a new diagnosis of OUD.

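### Baselines for H2.9–H2.15 may be taken after the STOP video or PCP advice, yet the pain change score, the H2.9 adjustment and the SAP 7.4 covariates treat them as pre-treatment

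*Protocol*

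**What the plan says.** **Order at the visit.** Protocol 10.6.2 gives two routes. If the PCP is seen as part of the baseline visit, patients see the PCP, and then "they will view the Video Doctor after they see their PCP and before they complete the baseline assessments". If not, "the RC/RA will show them the Video Doctor after consent and enrollment"; the order relative to the questionnaires is not stated for that route.

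**Late forms.** Protocol 10.4 names demographics, mental health, sleep, social support, quality of life and service use as post-visit forms: "These assessments may be completed up to three weeks after the baseline visit". It adds that most will be done the same day or within a week.

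**Safeguard.** The same section moves the items thought most responsive to advice into the prescreener: "Assessments that are most sensitive to change based on the brief advice delivered by the video doctor and/or PCP are included at the end". SAP 3.3.4 lists these as the monthly survey, TAPS, COMM and readiness items, and says "all other baseline values are collected at the screening and baseline visits". The CIDI is given at eligibility screening (Protocol 11.4.3). Provider outcomes use chart data from the 12 months before baseline (Protocol 11.5.12).

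**Use in the analysis.** SAP 7.8 compares arms on "Changes in pain-related symptoms and functioning from baseline as measured by the BPI", with a noninferiority margin of 1. For H2.8 and H2.9 it states: "Treatment effect is estimated adjusting for baseline level of each measurement". SAP 7.4 lists baseline scores as candidate covariates for the primary outcome, with the aim "to provide an unbiased estimate of the true treatment effect".

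**The concern.** A baseline is useful for change scores or adjustment because the intervention cannot have affected it. A form completed after the PCP's opioid advice or the opioid video has lost that guarantee. The exposure differs by arm: EUC patients watch a cancer-prevention video, receive an overdose-prevention handout, and have no further study intervention (Protocol 10.6.1). A STOP form completed late in the three-week window may also follow a same-day nurse visit, PCP advice given within 10 business days, and the first coaching call at about week 2.

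Three planned results are at stake.

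- **H2.11, pain.** Early worsening in STOP would enter the baseline and be subtracted out. That moves the test toward noninferiority, the unsafe direction.
- **H2.9, alcohol and drug use disorder.** Adjusting for a shifted PDSQ value removes part of any arm difference, or adds to it.
- **SAP 7.4, supplemental primary model.** If more than 10 covariates remain, step 4 selects among them by imbalance between arms. A score that STOP had already moved would be more likely to be chosen. The adjusted estimate is then used to judge how robust the primary conclusion is.

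**Working it through.** The documents give no figure on this point, so there is none to reproduce. The primary model uses only site and the prescreener baseline (SAP 7.2.2, 3.3.4), so sample size and power are untouched.

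**1. Which baselines are exposed**

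- Before exposure: primary, H1.2 and H2.1–H2.7 (prescreener), H2.8 (CIDI at screening), H3.1–H3.4 (prior chart data).
- Possibly after exposure: H2.9–H2.15, which is 7 hypotheses.
- Share: 7/15 = 47% of patient-level secondary hypotheses; 7/19 = 37% with Aim 3; 7/20 = 35% with H1.2 as well.
- By patient-reported instrument: about 10 of 14. Exposed are PDSQ, overdose risk, non-fatal overdose, BPI, PROMIS anxiety, PHQ-8, PSS, sleep, SF-12 and ED/hospital use. Not exposed are the opioid and non-opioid monthly items, COMM and CIDI.

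**2. Where the SAP uses an exposed baseline**

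- H2.11: change from baseline, stated.
- H2.9: baseline adjustment, stated.
- H2.10 and H2.12–H2.15: arm means compared, no baseline term stated. The general wording in Protocol 14.6 leaves one possible.
- SAP 7.4 Table 3: 9 of 19 rows are baseline-visit scores (alcohol use disorder, drug use disorder, overdose risk, two pain scores, anxiety, depression, sleep, quality of life).

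**3. How much of the recall period could follow the visit**

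Share = min(1, lag ÷ recall window). Windows are from Protocol 11.5 (the two weeks for PHQ-8 is from SAP 7.8); six months is taken as 182 days.

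| Form | Same day | 7 days | 21 days |
|---|---|---|---|
| Overdose risk, non-fatal overdose, ED/hospital (6 months) | 0 | 7/182 = 4% | 21/182 = 12% |
| SF-12 (4 weeks) | 0 | 7/28 = 25% | 21/28 = 75% |
| PDSQ, PHQ-8, PSS ideation (2 weeks) | 0 | 7/14 = 50% | 100% |
| PROMIS anxiety, sleep (7 days) | 0 | 100% | 100% |
| BPI (24 hours) | 0 | 100% | 100% |

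On the same day, the recalled period essentially precedes the advice and only reporting could shift. Protocol 10.4 does not name PDSQ, overdose risk, non-fatal overdose or BPI among the late forms, so their 7- and 21-day entries are conditional on a delay.

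**4. Size of the bias**

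Let d be the early shift in the baseline value, STOP minus EUC. A change score is off by −d. A linear baseline-adjusted estimate is off by −(slope × d), where slope is the regression of follow-up on baseline. For pain, higher is worse. If D is the true follow-up difference, the test in effect asks whether D − d < 1, that is, D < 1 + d.

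The d values and slopes (0.3 to 0.7) below are assumptions; the documents give neither.

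| Assumed d (BPI points) | Change score off by | Adjusted estimate off by | Effective margin |
|---|---|---|---|
| 0.1 | 0.1 | 0.03–0.07 | 1.1 |
| 0.2 | 0.2 | 0.06–0.14 | 1.2 |
| 0.3 | 0.3 | 0.09–0.21 | 1.3 |

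If d = 0 the bias is 0. If d is negative (early relief in STOP), the effective margin falls below 1 and the test is harder to pass. For H2.9, fitted by GEE, the adjusted column shows only the form of the bias, not its size.

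**The case against.** The plan anticipated the issue. It moved the items it considered most responsive to advice into the prescreener and left the others until later so as not to hold up clinic flow. The PCP's advice takes about 3 minutes and the video about 2, and most late forms are expected within a week. This stands, and it is why no effect on these scales can be assumed. The safeguard is incomplete, though. Protocol 11.0 names overdose behavior with substance use as most open to stigma and social-desirability bias, yet the overdose-risk and PDSQ forms are not in the prescreener.

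The placement of PDSQ, overdose risk, non-fatal overdose and BPI is also less certain than that of the other forms. In the available text of Protocol Table 6, the marks cannot be assigned to its pre-PCP and post-PCP columns, so their timing rests on Protocol 10.6.2 and SAP 3.3.4. If the formatted table marks them pre-PCP, it conflicts with 10.6.2 and the two must be reconciled. The exposed set would then shrink to H2.12–H2.15, H2.9 and H2.11 would drop out, and 9 − 5 = 4 rows of the SAP 7.4 table would remain affected (anxiety, depression, sleep, quality of life).

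A reader might infer that most secondary outcomes have a contaminated baseline. Counted by instrument that is roughly so; counted by hypothesis it is 7 of 15, and only two of those seven have a stated baseline term.

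Finally, SAP 7.4 is supplemental, so the primary result does not depend on it. That is correct and limits the weight of the point.

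**Conclusion.** The point holds in limited form and is a cheap improvement. Baselines for H2.9–H2.15 may follow arm-specific contact, and the SAP relies on such values as pre-treatment in the H2.11 change and noninferiority test, the H2.9 adjustment, and up to 9 of 19 candidate covariates in 7.4. The primary analysis, H1.2, H2.1–H2.8, Aim 3 and power are unaffected.

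It is tempting to go further and say that these analyses subtract part of the STOP effect. The documents do not support that. It requires an early effect on these particular scales, for which they give no size or sign. The sign could also go the other way: if risk counseling raised distress scores before the form was completed, a change score would overstate later improvement. An adjusted model would in any case remove only the slope times the shift.

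The effective margins of 1.1 to 1.3 rest wholly on assumed shifts of 0.1 to 0.3 points. What does not depend on those values is the direction for pain: if STOP worsens pain early, the planned test leans toward declaring noninferiority.

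**What to change.** **SAP 7.4.** Restrict candidate covariates to values obtained before any arm-specific contact (prescreener items, CIDI) and demographics, which brief advice could not plausibly alter. Do not let step 4 select on imbalance among post-exposure scores. Cost: fewer covariates and possibly less precision.

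**SAP 7.8, H2.11 and H2.9.** Keep the planned analyses and add one sensitivity analysis for each. Either limit it to participants whose baseline form preceded exposure, or compare follow-up values without the post-exposure baseline.

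- The restricted version will be smaller. At integrated visits, the order in Protocol 10.6.2 leaves few or no eligible forms. It is also hard to define equally in both arms, because SAP 6.2 says EUC video viewing is not held in the data system.
- The follow-up-only version avoids both problems. It gives up protection against chance baseline imbalance, which SAP 5.2 expects under PCP-level randomization.

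**SAP 3.3.4.** State for each instrument whether its baseline precedes or may follow the video and advice. Reconcile Protocol Table 6 with 10.6.2.

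**Conduct.** Where visits are still to occur and no PCP appointment forces the order, collect the self-administered battery before the video and record form and contact times. SAP version 2.0 is dated May 2025, so this may no longer be possible. The SAP changes need no new data where form dates exist.
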